3.2 Secondary Objectives

None

4. Study design/methodology

This study will be registered in Clinical Trials (clinicaltrials.gov) with the primary endpoint being a difference in IVH incidence and severity. We propose to conduct a randomized controlled trial in preterm infants (gestational age $\leq 30\ 6/7$ weeks) comparing the use of the Turtle Midliner and the standard of care practice (Control group). While blinding of study groups is always desirable in randomized studies, this will not be possible for this study.

Study Procedure

After eligibility of the infant is determined and the study informed consent is obtained from the parent or legal guardian, subjects will be randomized.

Randomization will follow a block randomization table that will determine if the infant will go into the group that will be positioned using the Turtle Midliner (Treatment Group) or not (Control Group).

All clinical care will be provided with consideration of the gestational age of the subject and follow NICU department guidelines and as ordered by physician and/or ARNP providers.

The key distinction for this study will be the use of the Turtle Midliner as a positioning aid in addition to standard of care for the Treatment Group, as opposed to solely standard practice of nesting and the use of rolls and other aids for the Control Group.

Treatment Group

The application and maintenance of the Turtle Midliner is within the scope of practice and skill-set of the NICU nursing and ancillary staff. The device has been in use in the WPH NICU since May 2016 when ordered by physician or nurse practitioner.

The use of the Turtle Midliner will be in addition to the NICU department process guidelines for positioning relevant to the gestational age of the subject. The Turtle Midliner will be applied no later than 3 hours following birth under the supervision of a

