Procedures and conditions that may contribute to IVH will be collected, such as: sepsis (positive blood culture, vasopressors, steroids, bolus administrations (fluids/meds), hypoglycemia (serum glucose <45) or hyperglycemia (serum glucose >200), hypercarbia (CO₂ >65mmHg), apnea/bradycardic episodes requiring stimulation, patent ductus

arteriosus, maximum respiratory support, suction events, line placements (PICC, IV, UAC/UVC) and/or needle punctures, UAC/UVC line collections, chest tube insertion, and any other noxious event

The subjects in both groups meet criteria for a standard of care head ultrasound at 6-8 days of life. Results from the head ultrasound report will be captured.

Clinical Outcomes Data – collected through date of discharge

The results of the last head ultrasound and/or magnetic resonance imaging (MRI) of the brain before discharge will be collected if these additional tests were ordered during the hospitalization (as solely determined by the attending neonatologist and not for study purposes).

Outcome data will include: days on mechanical ventilation throughout hospital stay, discharged home with G-Tube, discharged home on respiratory support (FiO₂, mode/settings), discharged with shunt, and length of stay (# days).

Adverse Event/Serious Adverse Event

The device, Turtle Midliner, solely impacts the skin contact areas. Only adverse events related to skin breakdown requiring wound care consultation with treatment will be reported as an adverse event. The principal investigator will evaluate adverse events related to skin integrity.

Any death will be reported as a serious adverse event according to Orlando Health IRB policy.

Major Protocol Deviation

For the purpose of this study, the midline position will be maintained with consistent use of the Turtle Midliner for all randomized study subjects in the treatment group (Turtle group) from ≤ 3 hours to 72 hours from birth. If the device is not utilized for a period greater than 30 consecutive minutes, the situation will be evaluated by the principal investigator. A major protocol deviation will be reported if the device was not in place for any reason other than the safety or well-being of the subject.

Study Endpoint

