5.1 Inclusion Criteria

1. Gestational age less than or equal to 30 6/7 weeks at birth
2. Less than 3 hours from birth
3. Informed consent obtained from parent or legal guardian prior to reaching time point for randomization

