5.2 Exclusion Criteria

1. Presence of genetic/chromosomal abnormality, congenital hydrocephalus, congenital neuromuscular disorder, or other diagnosis determined to impact survival or generalizability of results
2. Unable to participate for any reason based on the decision of the principal investigator.
3. Infants born outside Winnie Palmer Hospital for Women and Babies

6. Study Duration/ Study Timeline

Projected start date approx. April 2018 following IRB approval)

- | | | |
|-----------|---|-----------|
| • Stage 1 | Enroll subjects following IRB approval through April 2020 | 24 months |
| • Stage 2 | Data analysis through July 2020 | 3 months |
| • Stage 3 | Poster, abstract and/or manuscript through January 2021 | 6 months |

7. Statistical Analysis Plan

Sample Size Determination:

A sample size of 142 neonates with 71 in each group (71 in control group and 71 in intervention group) was determined in order to achieve 80% power to detect a 20% difference in IVH between the two groups, using a target rate of IVH of 15% in the intervention group. The test statistic used was the two-sided Z test with pooled variance. The significance level of the test would be 0.05.

We aim to allow for an additional 5% in sample size to adjust for either voluntary or involuntary withdrawal of some of the enrolled subjects. Upon reaching 142 enrollees the data will be reviewed. If any baby (ies) within the first 142 enrollees was withdrawn, the baby will be replaced according to the original randomized group, up to an additional 8 babies to ensure the power of the study and maintain a balance between the groups. A maximum of 150 babies will be enrolled.

Data Analysis:

Data analysis will include descriptive statistics with means and proportions. Comparative statistics will be used to compare IVH outcomes in the two groups. IVH outcome will be

determined by a reduction in the rate and/or severity of IVH. Any additional information on data points may be described in tables and/or graphs.

8. Informed Consent Process

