The patient's parent or legal guardian will be approached by the principal investigator or sub-investigator and the study will be explained in clear, layperson language. All study procedures will be disclosed. Risks to the patient will be explained; no individual patient benefits will be promised. The patient's parent or legal guardian will be given the opportunity to ask questions and confer with family members and others. If the patient's parent or legal guardian elects to consent to the trial, he/she will sign and date the consent form.

The original signed form will remain with the investigator in the study file; a copy will be given to the parent or legal guardian and a copy will be filed in the official medical record as well.

9. Privacy and Confidentiality

Federal regulations at 45 CFR 46 111 (a) (7) requires that when appropriate, there are adequate provisions to protect the privacy of subjects and to maintain the confidentiality of data. To maintain confidentiality, only the study investigators and regulatory coordinator will have access to the case reports and subject records. All records will be kept in a locked, password-protected computer as well. All paper case report forms and source documents will be maintained in a secured area within a locked office and maintained for a minimum of three years after the completion of the study.

10. Risk/Benefit

This study involves a product, the Turtle Midliner, already on the market and available for commercial use for prevention of cranial asymmetry and head preference in infants 0 to 6 months of age. The product being evaluated is a breathable, cotton, Lycra and foam beanie device, with two positioning rolls. The Turtle Midliner has been in use in the WPH NICU since May 2016.

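### Withdrawn babies are replaced in the arm they left, so up to 8 of at most 150 babies would get their arm from the withdrawal pattern and not from the block table: a small, conditional route to selection bias that is cheap to close

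*Combined protocol and SAP*

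**What the plan says.** Section 4 (Study Procedure) gives the allocation rule: "Randomization will follow a block randomization table that will determine if the infant will go into the group". On blinding of the groups, Section 4 says that "this will not be possible for this study". Section 5.1 requires "Informed consent obtained from parent or legal guardian prior to reaching time point for randomization".

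Section 7 (Sample Size Determination) sets 71 babies per group and then adds a second rule. "Upon reaching 142 enrollees the data will be reviewed", and for any baby withdrawn among those 142, "the baby will be replaced according to the original randomized group, up to an additional 8 babies". The stated aims are to protect power and keep the groups balanced, with a ceiling of 150. Section 1.4 anticipates 75 per group at that ceiling.

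Two other provisions decide who enters. Under Section 8 the parent or guardian "will be approached by the principal investigator or sub-investigator". Section 5.2 excludes a baby who is "Unable to participate for any reason based on the decision of the principal investigator".

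No section randomises the replacement places, puts them in random order or conceals them. No section describes concealment for the first 142 babies either.

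**The concern.** On its plain reading the replacement rule departs from the block table: the arm of each replacement is inherited from a withdrawal that has already happened. The requirement for consent before randomisation then protects little, because the arm may be fixed before the parents are approached.

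What is at stake is selective entry. A recruiter who knows that the next place is in the device arm could, without intent, approach or accept babies of lower or higher risk. Risk is partly visible at birth: Section 2 says that it is highest at the lowest gestational ages, and gives about 45% IVH at 500-750 g against 20% in very low birth weight infants. Replacement restores the head count, but babies chosen with knowledge of their arm do not restore comparability.

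**Working it through.** **1. The plan's own figure.** Inputs from Section 7: 15% IVH in the device arm, a 20% difference, two-sided 0.05, 80% power, pooled Z test. Read as 20 percentage points, the control rate is 35% (derived, not stated).

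n per arm = [1.96 × √(2 × 0.25 × 0.75) + 0.842 × √(0.35 × 0.65 + 0.15 × 0.85)]² / 0.20² = (1.200 + 0.501)² / 0.04 ≈ 72.4, so 73.

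Exact enumeration of the same test gives 79.7% power at 70 per arm and 80.4% at 71, so 71 is reproduced. For withdrawal, 142 / 0.95 = 149.5, so 150.

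**2. Share affected.** At most 8 / 150 = 5.3% of babies. Arm-matched replacement reaches the 75 per group of Section 1.4 only if eight withdrawals split 4 and 4. If all eight leave one arm, 79 v 71 are enrolled.

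**3. How many arms could be known in advance.** Assume that withdrawal is equally likely in either arm, that places are filled in random order, and that the recruiter knows which places are open. An arm is certain once all remaining places are in one arm. The expected number of such places with k replacements is 1 + 1/2 + … + 1/2^(k−1) = 2 − 2^(1−k):

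- k = 1: 1.0
- k = 2: 1.5
- k = 4: 1.88
- k = 8: 1.99

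If all eight places are in one arm, all eight are certain; the probability is 2 × 0.5⁸ = 0.8%.

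**4. Effect on error.** Assumptions, not in the documents: no true effect, 35% IVH in both arms, 71 analysed per arm, withdrawn babies of average risk, and k replacements of risk s, all in the device arm. The shift in the difference is k × (0.35 − s) / 71. Error rates are exact: device arm Bin(71 − k, 0.35) + Bin(k, s), control arm Bin(71, 0.35), pooled Z with critical value 1.96.

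| k | s | Shift (points) | False result favouring device | Favouring control | Two-sided |
|---|---|---|---|---|---|
| 0 | – | 0 | 2.52% | 2.52% | 5.04% |
| 2 | 25% | 0.28 | 2.74% | 2.32% | 5.06% |
| 2 | 15% | 0.56 | 2.96% | 2.13% | 5.09% |
| 4 | 25% | 0.56 | 2.97% | 2.14% | 5.10% |
| 4 | 15% | 1.13 | 3.46% | 1.79% | 5.25% |
| 8 | 25% | 1.13 | 3.48% | 1.80% | 5.28% |
| 8 | 15% | 2.25 | 4.68% | 1.24% | 5.93% |

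Low-risk replacements in the control arm give the mirror image. A 4/4 split with the same selection in both arms gives no shift. A 4/4 split with opposite selection (15% device, 55% control) gives 4 × 0.20 / 71 + 4 × 0.20 / 71 = 2.25 points and 5.84%. Eight device-arm replacements with no IVH risk at all (a 35-point gap) give 7.7%.

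**5. Power if the extra babies come from the table.** Exact, 35% v 15%:

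- 71 v 71: 80.4%.
- 75 v 75 (150 enrolled, no loss): 81.9%.
- All eight withdrawals in one arm and eight further babies split 4/4: 71 − 8 + 4 = 67 in that arm and 75 in the other. Power is 79.6% if the device arm has 67 and 79.7% if the control arm has 67.

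**The case against.** The strongest reply is that the rule adds little to a weakness that runs through the whole trial. Concealment is described for no baby. If staff knew a fixed block size (an assumption), the expected number of certain assignments in a block of 2m would be 2m/(m + 1): 1.33 per block of 4, 1.5 per block of 6, 1.6 per block of 8. That is about 47, 36 or 28 of the first 142 babies, against at most about 2 on average from the replacement rule. Eight further entries from known blocks would give about 2.7, 2.0 or 1.6 certain arms, so going back to the table does not by itself gain unpredictability. Balance is also a legitimate aim.

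Much of this stands. Most of the gain depends on concealment, and the fix must say so. It does not rescue the rule. When the withdrawals are all in one arm, shuffling or concealing the places cannot hide the next arm from someone who knows where they are; drawing from the table removes that link.

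Four stronger readings are tempting and not supported:

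- That eight babies will be assigned without randomisation. Eight is a ceiling, and the documents give no expected withdrawal pattern.
- That recruiters will always know the last replacement's arm. The plan does not say who performs the review or who learns the withdrawn arms. Section 9 gives investigators access to the case reports, so knowledge is plausible but inferred.
- That eight replacements in one arm is the worst case. Opposite selection in a 4/4 split gives the same shift, and larger risk gaps give more.
- That the same amendment can settle the analysis of withdrawn babies through the routine scan. Section 4 does say that "The subjects in both groups meet criteria for a standard of care head ultrasound at 6-8 days of life", but its Study Endpoint text stops outcome collection at withdrawal. Using a later scan would change that rule and probably the consent terms. It is a separate question.

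**Conclusion.** The point holds and is minor. Section 7 states a rule, not merely a gap, and the rule takes the arm of up to 8 babies away from the randomisation. Harm requires three things together: withdrawals, a recruiter who knows the open places, and selective entry. Without withdrawals or without selective entry the bias is zero, and its direction cannot be known from the documents.

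Under the assumed risk gaps the effect on two-sided error is slight. It is nearly nil with two replacements and under 1 percentage point with eight in one arm and a 20-point gap. In that last case the one-sided chance of falsely favouring the device goes from 2.5% to 4.7%, which is the more telling figure. All these sizes rest on the assumed 35% base rate and the assumed gaps. The reason to act is that the rule gains almost nothing in power and can be removed cheaply.

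**What to change.** In Section 7, delete the arm-specific replacement rule. Use the review at 142 only to count withdrawals, and assign that many further babies, to the existing maximum of 150, from the next entries of the block table in Section 4.

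In Section 4, state for all babies, not only the last 8, that each assignment stays concealed until eligibility and consent are recorded, and that enrolling staff do not know the block size.

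The cost is wording, a table that runs to 150 and a concealment step. The maximum enrolment does not change. The downside is that evaluable numbers may differ slightly between arms; in the 67 v 75 case the loss against 71 v 71 is under 1 point of power. Whether withdrawn babies are analysed should be settled separately and is not part of this change.

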1.6 Primary Objective

The primary objective of this study is to determine if infants positioned with the Turtle Midliner to optimize midline head positioning will have a better IVH outcome, determined by a decrease in rate of occurrence or severity of IVH, when compared to infants receiving the standard care (control group) with no Turtle Midliner intervention.

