Therefore, we are aiming to conduct a prospective randomized controlled trial in order to answer the research question: Does early use of the Turtle Midliner reduce the incidence and/or level of severity of intraventricular hemorrhage if used in infants born at $\leq 30 \frac{6}{7}$ weeks and neutral position is maintained for the first 72 hours of life? We hypothesize that the use of early consistent neutral positioning compared to the standard care (nested positioning) practiced in the NICU will reduce the risk of intraventricular hemorrhage in preterm infants born at $\leq 30 \frac{6}{7}$ weeks and have a positive effect on the incidence and/or level of severity of intraventricular hemorrhage in this population.

3. Objectives

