3.1 Primary Objective

The prime objective is to determine if early application of the Turtle Midliner for preterm infants, ≤ 3 hours following birth and with subsequent continuous use through 72 hrs. of life to ensure maintenance of optimal midline positioning (treatment group), will impact the IVH outcome as determined by a reduction in the rate and/or severity of IVH when compared to infants receiving the standard regimen of care (control group).

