The study period will be the first 72 hours of life with data collection for clinical outcomes to continue until discharge from the hospital, transfer to another institution, removal or withdrawal from the study, or death. There will be no additional contacts or follow-up for subjects beyond those time points.

The primary endpoint for the study is the difference in IVH incidence and severity between the two groups from birth through the first 72 hours of life.

5. Study Population

Each study subject must meet all of the indicated inclusion criteria and none of the exclusion criteria noted below:

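### Either a lower IVH rate or lower IVH severity can count as success, with no operational severity measure, test, order or adjustment, and the endpoint wording elsewhere in the protocol differs

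*Combined protocol and SAP*

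**What the plan says.** Three places let either component suffice:

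- Section 1.6: a better outcome is "determined by a decrease in rate of occurrence or severity of IVH".
- Section 3.1: the device "will impact the IVH outcome as determined by a reduction in the rate and/or severity of IVH when compared to infants" on standard care.
- Section 7, Data Analysis: the IVH outcome is "determined by a reduction in the rate and/or severity of IVH".

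The research question in Section 2 also joins incidence and severity with and/or. The hypothesis that follows it is mixed. It first predicts a lower risk of IVH and then adds that positioning will "have a positive effect on the incidence and/or level of severity of intraventricular hemorrhage in this population".

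Section 4 is worded differently. On registration: "This study will be registered in Clinical Trials (clinicaltrials.gov) with the primary endpoint being a difference in IVH incidence and severity". Under Study Endpoint: "The primary endpoint for the study is the difference in IVH incidence and severity between the two groups". Either sentence may simply describe what is measured, or may mean that both parts must improve.

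On method, Data Analysis says "Comparative statistics will be used to compare IVH outcomes in the two groups" and names no test. The two-sided pooled Z test, the 0.05 level and the 80% power all appear in the sample-size paragraph, for one IVH proportion. Severity is described only in the Section 2 background, which mentions four grades. Sections 1.7 and 3.2 list no secondary objectives, so severity sits only in the primary question. Section 4 states "While blinding of study groups is always desirable in randomized studies, this will not be possible for this study".

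**The concern.** A rule that accepts either of two comparisons, each at 0.05, gives a false claim of benefit more chances than the single test the trial was sized on. How many more depends on what severity means. It could be grade 0-IV in all infants, the proportion with grade III-IV, or grade among infants who bleed, and the plan does not commit to any of these. Because the groups are unblinded, nothing in the plan stops that choice from being made once results by arm are known. A success on severity alone would then rest on a comparison with no pre-stated measure, test, level or power.

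If Section 4 is taken to require both parts, the problem is reversed. Error is not inflated, but the power calculation no longer describes the chance of success. On neither reading could a second statistician reproduce the primary analysis from the text. This is the trial's only objective.

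**Working it through.** **1. The plan's own figure.** Inputs from Section 7: 15% in the intervention group, a 20% difference, two-sided 0.05, 80% power, pooled Z, 71 per group. Reading the difference as 20 percentage points gives 35% in controls and a mean of 25%.

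n = [1.96·√(2·0.25·0.75) + 0.8416·√(0.35·0.65 + 0.15·0.85)]² / 0.20² = (1.200 + 0.501)² / 0.04 ≈ 72.4, so 73 per group.

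At 71 per group this formula gives 79.2% power. The exact binomial power of the pooled Z test is 80.4%, so 71 per group is reproduced. It covers the any-IVH rate only.

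**2. A bound by hand.** If rate and severity were independent tests, the two-sided error would be 1 − 0.95² = 9.75%, and 1 − 0.975² = 4.94% in the direction of benefit. Positive correlation between the tests brings it down towards 5% and 2.5%.

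**3. Error if either part suffices.** The documents give no grade mix, so these splits for grades 0/I/II/III/IV, the same in both arms, are assumptions:

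- S1: .65/.15/.10/.05/.05
- S2: .75/.10/.07/.04/.04
- S3: .80/.08/.06/.03/.03

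Each scenario used 71 per arm, 400,000 simulated trials and a critical value of 1.96. Proportions were compared by pooled Z and grades by tie-corrected Wilcoxon. Entries are two-sided % / % in the direction of benefit.

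| Rule | S1 | S2 | S3 |
|---|---|---|---|
| Any IVH alone | 5.05 / 2.52 | 5.19 / 2.58 | 5.09 / 2.54 |
| Rate or ordinal grade, all infants | 6.06 / 3.02 | 5.85 / 2.91 | 5.56 / 2.78 |
| Rate or grade III-IV | 9.32 / 4.64 | 9.49 / 4.71 | 9.19 / 4.60 |
| Rate or grade among affected | 9.75 / 4.90 | 9.88 / 4.96 | 9.85 / 5.02 |
| Rate or best of the three, picked afterwards | 12.89 / 6.48 | 12.80 / 6.41 | 12.62 / 6.40 |

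The fourth row sits at the independence bound of step 2.

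Over 25 wider assumed splits (IVH rate 15-45%), a fixed severity test gives 5.2-10.0% two-sided (2.6-5.1% towards benefit). Picking the best of three gives 11.6-13.9% (5.9-7.0%). A separate set of assumed splits puts the fixed-test range at 2.6-5.2% towards benefit. Lengthening the menu of severity tests raises the picked-afterwards figure to 6.8-7.6%.

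**4. Power if both parts are required.** Control is S1 and the intervention rate is 15%. Three assumed effects let severe grades fall at least in proportion to the rate:

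- (a) .85/.064/.043/.0215/.0215
- (b) .85/.075/.054/.0105/.0105
- (c) .85/.09/.06/0/0

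Power for both parts under (a), (b) and (c), against 80.3-80.5% for the rate alone:

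- ordinal, all infants: 77.7, 79.4, 80.3%
- grade III-IV: 24.9, 47.1, 76.5%
- grade among affected: 1.8, 6.3, 20.7%

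If the benefit falls mainly or wholly on mild bleeds (.85/.03/.02/.05/.05 or .85/.05/.02/.04/.04), power for both with the ordinal test drops to about 69-74%.

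**5. A single ordinal primary test.** Two-sided error is 4.9-5.0%. Power is 78.8, 81.9 and 85.1% under (a) to (c), and 69.4% and 74.0% under the two effects on mild bleeds.

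**The case against.** The strongest reply has four parts.

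- **The documents do not settle on either-or.** A reader might infer one consistent rule. The endpoint statements in Section 4 say incidence and severity, and the Section 2 hypothesis puts risk reduction first. This stands: the documents conflict, and inflation follows only on the either-or reading. That reading is nevertheless the one in the primary objective and the analysis section.
- **Severity is not wholly undefined.** Section 2 mentions four grades, and Appendix 15.1 lists a head ultrasound sheet that is not in the text supplied and may record grade. This also stands. What is absent from the text is an operational measure, meaning which infants, which scale or cut-off, and which test.
- **The worst case is hypothetical.** A reader might infer that the sponsor means to choose the severity test after seeing results. Nothing says so. Section 4 says only that study groups cannot be blinded, not who analyses the data or when. The 12-14% figure shows what the plan fails to prevent, not what it proposes. Likewise, the data review at 142 enrollees should not be read as an interim look at outcomes, because the only purpose given is replacing withdrawn infants.
- **The excess can be small.** With one fixed ordinal test in all infants, the added error is about 0.3-0.5 points towards benefit under S1 to S3. This is true, but the plan does not commit to that test.

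Choosing rate-first over a single ordinal test is partly a design preference. The defect itself requires only that one rule be fixed in advance.

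**Conclusion.** The concern holds and must be fixed. On the either-or wording, the false-finding rate exceeds the 5% (2.5% towards benefit) of the single rate test. It is about 5-6% (2.6-3.1%) with all-infant ordinal grade, and about 9-10% (4.3-5.2%) with grade III-IV or grade among affected infants. It is about 12-14% (6-7%, more with a longer menu) if the test is chosen afterwards. If both parts are required, error is not inflated, but power is about 69-80% with the ordinal test and far lower with most other measures.

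All of these figures rest on assumed grade splits and effects and on an illustrative menu of tests. They show the order of magnitude and are not estimates for this trial. The case for change does not depend on the largest of them. The primary question has two incompatible wordings, and one component has no stated analysis.

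**What to change.** Before any outcome by arm is seen:

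1. Name one primary comparison: the proportion of randomised infants with any IVH (grade I-IV), two-sided pooled Z test at 0.05. The 71 per group already supports this if the 20% difference means 20 percentage points; the SAP should say so.
2. Make severity a key secondary outcome: grade 0-IV in all randomised infants, by one named rank or ordinal test. Test it for confirmation only if the primary is significant; otherwise report it descriptively.
3. State that both comparisons use the same one named head ultrasound, and how infants without that scan are counted. Section 4 sets the endpoint at birth to 72 hours but captures a scan at 6-8 days and any last scan or MRI before discharge, so the choice of scan is a further open route to selecting a result.
4. Use the same wording in Sections 1.6, 2, 3.1, 4 and 7, list severity in Sections 1.7 and 3.2, and update the registered endpoint.

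A single ordinal grade 0-IV primary test is an acceptable alternative. It also holds error near 5%, but its power at 71 per group is about 69-85% depending on whether severe grades fall with the rate, so it needs its own sample-size statement. Splitting alpha equally is less attractive: testing the rate at 0.025 would need 88 per group, or leave about 70% power at 71.

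The cost is a dated amendment and a registry update, with no new infants or data. Under rate-first, the trial gives up the possibility of claiming success on severity alone.
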